# 16. Protocol Procedures, Methods, and Duration of the Study—in nontechnical language

- Participants in this study will be randomized to two groups: One group will receive an intravenous (IV) dose of ketamine during the surgery. The other group will receive a normal saline placebo IV (control group). For the patients that are randomized to the ketamine group, the PI will submit an order for the ketamine to the research pharmacist. The pharmacist will determine the dosing of ketamine based on a standard calculation and prepare the syringe that will be used to dispense the ketamine. For both groups, the IV infusion will be discontinued at the conclusion of the surgery. Participants will receive standard anesthetic drugs and appropriate pain medication to control their postoperative pain in keeping with the current practice. We will compare recovery data including vital signs and pain scores as well as potential side effects of controlled versus study group. Approximately 24 hours after surgery, a patient assessment form will be completed ("24 Hr Post-Operative Data Collection Form") by the PI or research study team.
- b. What is the probable length of time required for the entire study (i.e., recruitment through data analysis to study closure)?
  Approximately two years
- Participants will be involved during surgery, during their recovery in the PACU, and at one time point approximately 24 hours postoperatively (to complete the Post-Operative Patient Satisfaction Assessment Form).
- d. If different phases are involved, what is the duration of each phase in which the participants will be involved? If no phases are involved, enter "not applicable." Not applicable
- **e.** List the procedures, the length of time each will take, and the frequency of repetition, and indicate whether each is done solely for research or would already be performed for treatment or diagnostic purposes (routine care) for the population. *Insert additional table rows as needed.*

Procedure	Length of Time	Frequency of	Doscorrah (Dos)
rioccarc			Research (Res) -
	Required of	Repetition	OR- Routine Care
	Participants		
Pregnancy testing for women of	<5 minutes	once	□Res ⊠Routine
childbearing potential			
Weight measurement	<5 minutes	once	□Res ⊠Routine
Normal Saline or Ketamine infusion	<three hours<="" td="">once	⊠Res □Routine	</three>	once	⊠Res □Routine
Monitoring and measurement of	From onset of	Continuously	□Res ⊠Routine
electrocardiogram, heart rate, blood	surgery until	during the stated	
pressure, respiratory rate, and	discharge from	time	
oxygen saturation	the PACU		
24 hr postoperative patient forms: 1)	<5 minutes for	Once	⊠Res □Routine
"Post-Operative Patient Assessment	each form		
Form" to be completed by the PI or			
study staff, and 2) "24 hour Post-			
Operative Patient Satisfaction			

- 1	Assessment Form" that will be completed by the subject	-		
f.	Will an interview script or questionnaire be used? If Yes , attach a copy.		⊠Yes □No	
g	
 
Will participants incur any costs as a result of their participation?
 
If Yes, describe the reason for and amount of each foreseeable cost.
 
			□Yes ⊠No cost.
h.	Will participants be compensate  If Yes, complete i-v:  i. Type: (e.g., cash, check, gift  ii. Amount or Value:  iii. Method (e.g., mail, at visit):  iv. Timing of Payments: (e.g., e.g.,	card, merchandis	nonth):	□Yes ⊠No

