#### 8.0 STUDY INTERVENTIONS/PROCEDURES

This is a prospective, randomized, double-blind, placebo-controlled single institution study. All patients will be provided written informed consent in the preop clinic prior to participation. Patients will be randomly allocated to the ketamine (K) study group or the control (C) group. Random allocation of patients will be performed by study coordinator using closed envelopes containing allocation group. All patients will be provided standard hospital care.

On the day of surgery, baseline oxygen saturation measurements will be recorded for each patient. The study coordinator will provide the attending anesthesiologist with a 30ml syringe containing either ketamine (K) 10mg/ml or saline (C). Both syringes will be labeled "Ketamine 10mg/ml" along with time and date of preparation by the pharmacy. In the operating room, standard ASA monitors will be used along with arterial and /or CVP monitoring according to the preference of the attending anesthesiologist. After adequate preoxygenation with 100% oxygen, general anesthesia will be induced with intravenous midazolam 2mg, fentanyl 100mcg and propofol, 2-3 mg/kg ideal body weight (IBW) followed by rocuronium 50mg before endotracheal intubation. IBW is calculated by the Hamwi Formula: men start with 106 lbs for first 5 feet + 6 lbs for each inch over 5 feet,

women use 100 lbs for first 5 feet + 5 lbs for each inch over 5 feet (Medium frame); for small frame (- 10%), large frame (+ 10%).

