Upon arrival in the PACU, all patients will be monitored according to standard post-anesthesia protocols for a period of at least 2 hours. The PACU nurse that is blinded to treatment group will assess and record baseline vital signs including HR, BP, RR, SpO2, and VRS score. Modified Aldrete score including presence of nausea/vomiting, sedation level or evidence of dysphoria will be recorded at 15 minute intervals. SpO2 will be monitored continuously with documentation of oxygen flow required to maintain oxygen saturation of at least 94%. As per PACU protocol, initially patients will receive oxygen 40% by open face mask, with weaning to NC or RA, maintaining SpO2 > 94%. Desaturation episodes will be scored automatically by pulse oximetry analysis software (Nellcor, NPB-290). Data evaluated will include: comparison of patient demographics, time to first analgesic, number of analgesic demands, amount of analgesic consumed in the OR and PACU, frequency of side effects, and ODI (oxygen desaturation index). ODI is defined as the number of desaturations (lower than 4% from baseline) per hour of recording, which correlates with PSGdetermined apnea/hypopnea index and can be used as an indicator of postoperative apneic episodes <Ahmad S, Anesthesia and Analgesia 2008>}. Time to first analgesia request will be recorded and pain (VRS >/= 4) will be treated with intravenous morphine 2mg. This will be repeated at 5 minutes intervals until pain score improves or patient has untoward side

effects, at which time the PACU physician should be immediately called to the patient's bedside. Further monitoring for of patients in PACU or on the floor may be indicated in some patients according to the discretion of the attending anesthesiologist and surgeon; however it is not mandatory for this study. According to Terris et al., "Significant complications [of OSA] generally emerge within 2 hours after surgery. Therefore a decision regarding the level of postoperative monitoring needed may be made with confidence during the period of time that the patient is in the recovery room" <Terris DJ, Laryngoscope 1998>.

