When patients are deemed suitable for discharge from the PACU, patients will be transferred to the floor where they will receive standard hospital care and monitoring including routine vital signs continuous pulse oximetry. At 24 hrs post-op, patient vital signs, VRS, and morphine usage will be assessed along with patient satisfaction related to overall anesthesia care according to a 5-point scale (1= very unsatisfied, 2=unsatisfied, 3=equivocal, 4=satisfied, 5=very satisfied).

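### The investigator's ketamine-only order reveals the arm, and the investigator may then complete the 24-hour assessment; no masked 24-hour assessor is required in a trial described as double-blind

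*Combined protocol and SAP*

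**What the plan says.** The combined document holds a protocol (sections 1.0 to 14.0) and a resubmitted Human Subjects Protocol (numbered items, of which item 16 covers procedures).

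- **Design.** Section 8.0: "This is a prospective, randomized, double-blind, placebo-controlled single institution study".
- **Allocation.** Section 8.0: "Random allocation of patients will be performed by study coordinator using closed envelopes containing allocation group". The coordinator also hands the syringe to the anesthesiologist. Ketamine and saline syringes carry the same label.
- **Ordering.** Item 16: "For the patients that are randomized to the ketamine group, the PI will submit an order for the ketamine to the research pharmacist". No order is described for the saline arm.
- **PACU assessment.** Section 8.0: "The PACU nurse that is blinded to treatment group will assess and record baseline vital signs". Desaturations are scored automatically by oximetry software.
- **24-hour outcomes.** Section 8.0: "At 24 hrs post-op, patient vital signs, VRS, and morphine usage will be assessed along with patient satisfaction". Neither the assessor nor the assessor's masking is named.
- **24-hour form.** The item 16 text says the form "will be completed ('24 Hr Post-Operative Data Collection Form') by the PI or research study team". The procedures table in item 16.e agrees: the assessment form is "to be completed by the PI or" study staff. The separate satisfaction form is one "that will be completed by the subject".

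**The concern.** An order placed only for patients randomized to ketamine tells the person placing it who is on ketamine. The absence of an order identifies the saline patients. That same person is a permitted 24-hour assessor. The coordinator, who allocates from the envelopes, is not barred from the role either.

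Lower pain scores are part of the hypothesis in section 4.0, and section 11.0 plans a Mann-Whitney test of VRS. The VRS is the patient's own report, but someone has to ask for it and write it down. If that person knows the arm, the recorded scores can drift towards the hypothesis with no drug effect. A reader of the final report could not tell which 24-hour scores were collected masked, and this cannot be repaired after collection.

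**Working it through.** **Who can know the arm, and who may assess**

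| Person | Route to the allocation | May complete the 24-hour form? | Stated to be masked? |
|---|---|---|---|
| Investigator | Arm-specific ketamine order (item 16) | Yes, named (item 16 and 16.e) | No |
| Study coordinator | Performs envelope allocation (section 8.0) | Not excluded; study team or staff | No |
| Anesthesiologist giving the infusion | None described; syringe labels are the same | Not excluded if on the study team | Through the label only |
| PACU nurse | None described | Not named for this task | Yes, in the PACU |

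The common label masks whoever gives the infusion. It cannot mask whoever placed an order that exists for one arm only. Item 23 of the Human Subjects Protocol reports changes to personnel and patient population on resubmission, not a change to the blinding, so the double-blind description still stands.

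**What is exposed**

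Of the four 24-hour items, satisfaction is completed by the patient, and morphine use and vital signs are the more objective items. The VRS is the one most open to influence from the person asking.

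**Illustration of size**

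The plan has no figure of its own to reproduce on this point.

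From the documents: 5% type 1 error, 32 per group and the Mann-Whitney test (section 11.0); 150 participants (item 15).

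Assumed:
- the test is two-sided (sidedness is not stated);
- the 150 are split equally, 150 / 2 = 75 per group (the split is not stated);
- scores are roughly normal, with Mann-Whitney efficiency 3/π relative to the t-test;
- there is no true effect;
- the recorded VRS shifts by b = 0.1 to 0.2 SD between arms because of unmasked recording.

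Formula: false-positive rate = P(|Z + b·√((n/2)·(3/π))| > 1.96).

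The multiplier √((n/2)·(3/π)) is √(16 × 0.955) = 3.909 for n = 32, and √(37.5 × 0.955) = 5.984 for n = 75.

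| n per group | b (SD) | Shift in Z | False-positive rate |
|---|---|---|---|
| 32 | 0.1 | 0.391 | 0.068 |
| 32 | 0.2 | 0.782 | 0.122 |
| 75 | 0.1 | 0.598 | 0.092 |
| 75 | 0.2 | 1.197 | 0.223 |

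If an unmasked person completes only half of the forms, the mean shift is b/2. The rates become 0.054 and 0.068 at 32 per group, and 0.060 and 0.092 at 75 per group.

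A simulation (20,000 runs, integer 0–10 score, assumed mean 4 and SD 2) agrees: 0.065 and 0.116 at 32 per group, 0.089 and 0.216 at 75 per group, and 0.048 with no bias.

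A fixed bias does more harm as n grows. This matters because planned enrollment went from 65 (section 6.0) to 150 (item 15).

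**The case against.** **Unmasking is an inference.** No text says the investigator is unmasked, and item 16 is written in lay language for the IRB. Saline syringes must also be requested somehow, perhaps by a route set out in the Drug Review Sheet, which is not in the available text. This limits certainty about what happens in practice. It does not change what item 16 says: the order is conditional on arm, and no step that would hide the arm is described.

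**Exposure is permitted, not prescribed.** A masked team member could complete every form and comply with the plan. That is true, and it is why the finding is a missing safeguard rather than a demonstrated bias.

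**The route to the VRS is not spelled out.** The contents of the form are not listed, and the 24-hour score could be copied from the ward chart. This stands as a limit. The plan does not say so, however, and it allots up to five minutes of participant time to each form.

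**The affected outcome is narrow.** The sample size rests on opioid requirement, and section 4.0 does not tie pain scores to 24 hours. This also stands, and it limits the weight of the point.

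**The size is assumed.** Correct: the documents offer no basis for 0.1 to 0.2 SD. The 32 per group also comes from the protocol, whereas the ordering text sits in the resubmission with 150 participants. The rates show sensitivity only, and the finding does not depend on them.

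**The investigator oversees the study (section 12.0).** Oversight does not require knowing each patient's arm, provided emergency unblinding is available.

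**Conclusion.** The concern holds. Followed as written, the ordering rule in item 16 defeats the blinding claimed in section 8.0 for someone who is expressly allowed to make the 24-hour assessment, and nothing in the document closes the gap. It should be fixed before further patients are assessed, but it does not undermine the trial as a whole.

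The conclusion about procedure rests on one inference: that an order described only for ketamine patients has no coded counterpart for saline patients. The practical effect also depends on an unmasked person completing the form and influencing the recorded score. Under the assumptions above, the nominal 5% error rate for 24-hour VRS becomes about 7–12% at 32 per group or 9–22% at 75 per group. If half of the forms are affected, it becomes about 5–7% and 6–9%.

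**What to change.** 1. In item 16, replace the ketamine-only order with one arm-neutral order (study drug: ketamine or saline) submitted for every randomized patient.
2. Send the allocation directly to the research pharmacist, who prepares identically labeled syringes for both arms. Reconcile this with the coordinator-and-envelope procedure in section 8.0, so that the two parts agree on who holds the allocation.
3. State in section 8.0 and item 16 that the investigator and anyone completing the 24-hour form have no access to allocation until database lock, except for emergency unblinding, and that anyone who handles allocation does not assess outcomes.

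The cost is a few sentences. The pharmacist is already in the plan, and no visit, dose or sample size changes. The pharmacy takes on the allocation list and the saline syringes, and the existing staff must keep allocation and assessment roles separate.

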#### 17. Describe the potential benefits of the research.

The benefit of participating in this study is the possibility that participants could have less pain and fewer complications after their general ENT or Orthopedic Surgery. Participants will have the opportunity to help in finding a better surgical management approach in adults with obstructive sleep apnea undergoing General ENT or Orthopedic Surgery. There is also the possibility of a recovery with fewer complications for other people general ENT or Orthopedic Surgery in the future.

#### 18. Risks

a. List the known risks—physical, psychological, social, economic, and/or legal—that participants may encounter as a result of procedures required in this protocol. Do not list risks resulting from standard-of-care procedures. Note. Risks included in this protocol document should be included in the written consent document.

Multiple studies have demonstrated that low-dose ketamine, when given with anesthetic induction agents and inhalational anesthetic gas, is safe and effective with few if any, adverse side effects.

#### Common adverse reactions include:

Hypersalivation, anorexia, nausea/vomiting, hypertension, hypotension, tachycardia, bradycardia, diplopia, nystagmus, fasciculations, depressed reflexes, and hallucinations. Common side effects are typically reversible with cessation of the infusion.

- **b.** Estimate the frequency, severity, and reversibility of each risk listed. Please see item 18.a.
- **c.** Is this a therapeutic study or intervention?

⊠Yes □No

If Yes, complete the following items:

- i. Describe the standard of care in the setting where the research will be conducted: Balanced general anesthetic with postoperative intravenous opioids.
- ii. Describe any other alternative treatments or interventions: N/A
- iii. Describe any withholding of, delay in, or washout period for standard of care or alternative treatment that participants may be currently using: None
- d. Do you foresee that participants might need additional medical or psychological resources as a result of the research procedures/interventions? ☐Yes ☒No If Yes, describe the provisions that have been made to make these resources available.

If No, provide justification for performing the research:\_\_\_\_

#### 19. Precautions/Minimization of Risks

**a.** Describe precautions that will be taken to avoid risks and the means for monitoring to detect risks.

Supportive medications and care will be provided to avoid or treat adverse effects experienced by participants.

# If study involves drugs or devices skip Items 19.b. and 19.c., go to Item 20, and complete the Drug or Device Review Sheet, as applicable.

- b. If hazards to an individual participant occur, describe (i) the criteria that will be used to decide whether that participant should be removed from the study; (ii) the procedure for removing such participants when necessary to protect their rights and welfare; and (iii) any special procedures, precautions, or follow-up that will be used to ensure the safety of other currently enrolled participants.

  Criteria for early withdrawal for the study: <2 hrs surgical time, any surgical or anesthetic complication that prevents the assessment of study variables, clinically relevant residual neuromuscular blockade or other reason for patient to require prolonged tracheal intubation following surgery.
- c. If hazards occur that might make the risks of participation outweigh the benefits for all participants, describe (i) the criteria that will be used to stop or end the entire study and (ii) any special procedures, precautions, or follow-up that will be used to ensure the safety of currently enrolled participants.

  The overall study will be suspended if is determined that, at any point, study procedures are not adequate to protect the participant's safety. All efforts will be made during procedures to ensure that the participant's risk is minimized.

#### 20. Informed Consent

- a. Do you plan to obtain informed consent for this protocol?
   ✓ If Yes, complete the items below.
   If No, complete and include the Waiver of Informed Consent or Waiver of Authorization and Informed Consent, as applicable.
- b. Do you plan to document informed consent for this protocol?
   ☑Yes ☐No
   If Yes, complete the items below.
   If No, complete the items below and include the Waiver of Informed Consent Documentation.
- c. How will consent be obtained? Consent will be obtained from the potential participant preoperatively during their evaluation in the PAC by a member of the research team named in this submission or named in later revisions/amendments.
- d. Who will conduct the consent interview? See above
- e. Who are the persons who will provide consent or permission? See above
- f. What steps will be taken to minimize the possibility of coercion or undue influence?

  Participation is voluntary and the potential participant will have every opportunity to ask any questions or raise any concerns and have those addressed to their satisfaction prior to obtaining and documenting consent.
- **g.** What language will the prospective participant or the legally authorized representative understand?  $\underline{\bf English}$
- h. What language will be used to obtain consent? English
- i. If any potential participants will be, or will have been, in a stressful, painful, or drugged condition before or during the consent process, describe the precautions proposed to overcome the effect of the condition on the consent process. If not, enter "no such effect."
  No such effect
- j. If any project-specific instruments will be used in the consenting process, such as flip charts or videos, describe the instrument(s) here, and provide a copy of each. If not, enter "not used."
  Not used
- k. How long will participants have between the time they are told about the study and the time they must decide whether to enroll? If not 24 hours or more, describe the proposed time interval and why the 24-hour minimum is neither feasible nor practical. The consent process will begin during the potential participant's preoperative visit to the PAC. Participants may not have more than 24 hours after learning of the study before documenting their consent to participate, but they will have additional days following screening and documentation of consent before the day or surgery and the implementation of any study specific procedures.

#### 21. Procedures to Protect Privacy

Describe the provisions included in the research to protect the privacy interests of participants (e.g., others will not overhear your conversation with potential participants, individuals will not be publicly identified or embarrassed).

Privacy will be ensured at all times. Conversations with potential participants will be conducted privately, usually in an exam room with a closed door to prevent others from overhearing the conversation. Individuals will not be publicly identified or embarrassed.

#### 22. Procedures to Maintain Confidentiality

- a. Describe the manner and method for storing research data and maintaining confidentiality. If data will be stored electronically anywhere other than a server maintained centrally by UAB, identify the departmental and all computer systems used to store protocol-related data, and describe how access to that data will be limited to those with a need to know.

  Participant data will be stored on a password-protected computer system maintained for human
  - Participant data will be stored on a password-protected computer system maintained for human subjects research purposes by the UAB Department of Anesthesiology. Access to this particular system is restricted to only certain members of the research team, based on their need to know. The list of patients participating in the study, including their medical record numbers and dates of surgery, will be kept separately and securely and will be destroyed after final data analysis. Any original paper records may be scanned and stored on the above mentioned departmental server and then shredded after they have been transferred to the password-protected computer system.
- b. Will any information derived from this study be given to any person, including the subject, or any group, including coordinating centers and sponsors? □Yes ⋈No
  If Yes, complete i-iii.
  i. To whom will the information be given? □
  ii. What is the nature of the information? □
  iii. How will the information be identified, coded, etc.? □

